Activated state of macrophages is mirrored by upregulation of the 18-kDa translocator protein (TSPO)¹²⁻¹⁴. Positron emission tomography (PET) with TSPO-specific ligands has been developed over the last few years and provides a novel *in vivo* molecular technique to detect macrophage activation¹⁵. However, results obtained by second-generation radioligands in preclinical models have not been consistently reproduced in humans¹⁵. Successively more promising PET radiotracers have been developed for this application¹⁶⁻²⁰. Recently, one of the newer agents, ER176 {4-(2-chlorophenyl)-N-(methyl- ^{11}C)-N-((1R)-1-methylpropyl)- 2-Quinazolinicarboxamide}, a third-generation TSPO-specific radioligand (**Figure 1**), has shown high affinity and excellent *in vivo* target-to-background binding^{21, 22}. Based on imaging data from several ^{11}C -labeled TSPO PET ligand studies, ER176 has been identified as the most suitable for *in vivo* study of activated macrophages due to: 1) a higher specific binding, 2) a smaller inter-subject variability, and 3) the unique ability to image even a low-affinity binding state²³. Delineation of activated macrophages with ^{11}C -ER176 PET in the stomach of patients with DG is a novel application. Mayo Clinic has an FDA-approved investigational new drug (IND) application (#149229) for use of ^{11}C -ER176 in a trial of neuroinflammation, which will be amended to include gastric imaging in DG and control participants proposed in this study.

The **overall goal** of this project is to demonstrate feasibility of dynamic ^{11}C -ER176 PET imaging to identify macrophage-driven immune dysregulation in gastric muscle of patients with DG. Non-invasive quantitative assessment with PET can significantly add to our diagnostic armamentarium for patients with diabetic gastroenteropathy. If a clear immune dysregulation is identified in a subset of patients, it can be targeted using immunosuppressive or immunomodulatory therapies. Furthermore, if validated, this imaging technique can facilitate clinical trials aimed at targeting immune dysregulation in DG, thus offering new therapies in a disorder with significant unmet need. We propose the following specific aim:

Specific Aim: To determine feasibility of dynamic ^{11}C -ER176 PET to identify macrophage-activation in diabetic gastroparesis

Hypothesis 1: Patients with diabetic gastroparesis demonstrate increased uptake for ^{11}C -ER176 in gastric body and antrum compared to matched controls

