Fig 3: Gastric muscular propria single cells on tSNE plots. **(A)** Overall immune cells (CD45⁺). **(B)** CD68⁺ cell subset, a marker for macrophage and phagocytic cell population. **(C)** TSPO⁺ cells closely overlapping with the CD68⁺ population suggesting macrophage subset of immune cells in gastric muscle express TSPO.

D. Research Design and Methods

We plan to recruit 4 patients with DG, 4 patients with diabetes without gastroparesis, and 4 age-matched healthy volunteers. Considering the clear higher prevalence of DG in females compared to males, in this pilot and feasibility study, we will recruit only females. DG patients and diabetic patients will be recruited using the inclusion and exclusion criteria listed in **Table 1**. Healthy volunteers will be screened to have no clinical history of diabetes or any GI symptoms. These will be screened using a simple GI questionnaire. Additionally, they will

be screened to have no inflammatory disorders of the GI tract or use of anti-inflammatory or immunosuppressive therapies. Participants will undergo a screening visit which will involve informed consent, history and physical

examination by the PI to ensure eligibility for participation in the study. Participants will also have a blood draw that will occur prior to the PET/CT scan. Participants will have 25 mL of blood drawn for PBMC isolation, proteomic, metabolomics, and genetic analysis. PBMCs will be isolated and their transcriptional and epigenomic profile will be studied. DG patients will complete a self-reported Patient Assessment of Upper Gastrointestinal Disorders Symptoms (PAGI SYM) questionnaire. This is composed of 20 items and 6 subscales to assess for symptoms of gastroparesis, dyspepsia, and gastroesophageal reflux disease. The severity of each symptom item over a 2-week recall period is scored from 0 (none or absent) to 5 (very severe). The

Gastroparesis Cardinal Symptom Index (GCSI)³⁷, a 9 symptom survey relevant to gastroparesis stratified in 3 subscales (nausea/vomiting, fullness/early satiety, and bloating) is contained within the PAGI-SYM. We will recruit DG patients with a score ≥ 3 suggesting moderate-severe symptoms. In the second visit, participants will present NPO after midnight and undergo the ¹¹C-ER176 PET/ CT scanning followed by upper endoscopy and biopsies. The imaging and endoscopy details are as below:

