Image analyses: PET and CT images will be transferred to a dedicated workstation (MIM Software Inc., OH). Image analyses will be done by a board-certified nuclear radiologist. Diagnostic image quality of the late PET images will be rated on a 5-point Likert scale. Ratings of ≥ 3 will be considered acceptable for diagnostic use whereas ratings of 1-2 will be considered unacceptable. On each PET image, volumes of interest (VOIs) will be

Table 1: Enrollment criteria for DG and Diabetic patients

Inclusion criteria	Exclusion criteria

 -Female - Ability to provide informed consent - Age 18-70 years - Type I or II diabetes mellitus - Clinical gastric emptying testing within 6 months of study enrollment (for DG patients only) -Gastroparesis defined by gastric retention of Tc-99m >20% at 4 hrs on scintigraphy (for DG patients only) - Average Gastroparesis Cardinal Symptom Index (GCSI) ≥ 3 suggesting moderate-severe symptoms (for DG patients only) 	
 - Women who are pregnant or cannot stop breast feeding for 24 hrs - Using anti-coagulants, anti-inflammatory medications (NSAIDs, corticosteroids, etc.) or immunosuppressive therapies within 4 weeks prior (for DG patients only) - Opioid use within last 4 weeks of gastric emptying scintigraphy (for DG patients only) - Prior gastric surgery - History of IBD, celiac disease, eosinophilic gastroenteritis, microscopic colitis

drawn around the stomach and other organs that may show radiotracer accumulation. The uptake in each VOI in each PET image will be measured and decay-corrected to the time of injection and normalized to the administered activity. The quantified VOI activity for all PET images will be converted to time-activity curves, and the retention of activity in each region will be used along with the IF to model the biodistribution of ¹¹C-ER 176. The radiopharmaceutical biodistribution will also be quantified by standard metrics [maximum & mean standardized uptake value (SUVmax and SUVmean respectively)]. The image quality, time-activity curves, and semi-quantitative metrics will be compared between diabetic gastroparesis patients and controls.

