Upper endoscopy with endoscopic ultrasound and targeted biopsies of gastric muscle: A pregnancy test will be administered to women of child-bearing potential. Upper endoscopy will be performed only on DG patients only. The endoscopy will be performed within 12 weeks of the participant's PET/CT scan, this will allow more scheduling flexibility for the participant and study team. During the endoscopy procedure an additional procedure known as endotracheal intubation may be performed to keep the airway open and assist with breathing. This will vary from case to case and is determined by the anesthesiologist assisting with or the physician performing the endoscopy. The echoendoscope (Aloka Arietta 850; Olympus, Center Valley, PA) will be advanced into the gastric lumen and a site targeted for EUS-guided core biopsies based on findings of the PET scan. Fine needle biopsy of the gastric wall will be performed using a 19 G needle (SharkCore; Medtronic, Minneapolis, MN) passed through the echoendoscope and across the entire gastric wall ensuring a full thickness (mucosa to serosa) core tissue sample. Sampling of the uninvolvled region will be done to serve as control. In patients who do not have clear signal on PET/CT, sampling will be done from gastric antrum and body to act as negative control. All endoscopic procedures will be done by advanced endoscopist [REDACTED] [REDACTED]. EUS-guided core biopsy is a safe procedure associated with a low risk of adverse events.

Assessment of gastric macrophages: After tissue dissociation, using technique similar to that shown in the preliminary data, cells will be sorted and profiled using the Fluidigm (San Francisco, CA) Helios cytometry by time of flight (CyTOF) mass spectrometry system. After cleanup in FloJo to obtain singlets, data will be analyzed using the R-based CytofKit tool^{38, 39}. In an approach that was not biased towards a limited subset of cell types, cellular subtypes will be identified and counted after labeling with a panel of 32 antibodies to distinguish monocytes and tissue myeloid cells from the other immune cells (CCR2, CD24, CD64, Ly6C, CD115/CSF1R, CD38, CD8a, Ly6G, CD11b (Mac-1), CD3e, CX3CR1, MERTK, CD11c, CD4, ESAM, PDL-1, CD14, CD44, F4/80, PDL-2, CD161 (NK1.1), CD45, FcER1, SiglecH, CD19, CD45R (B220), I-A/I-E, SIRPa (CD172a), CD206 (Mrc1), CD62L, IL2RA, CD25, TER-119). Data will be displayed as tSNE maps and heatmaps.

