- 2) Ability to provide informed consent
- 3) Type I or II diabetes mellitus
- 4) Gastroparesis defined by gastric retention of Tc-99m >60 % at 2 hrs and/or >10% at 4 hrs on scintigraphy (for DG patients only)
- 5) Average Gastroparesis Cardinal Symptom Index (GCSI) ≥ 3 indicating moderate-severe symptoms (for DG patients only)

Exclusion criteria:

- 1) Women who are pregnant or cannot stop breast feeding for 24 hrs
- 2) Using anti-coagulants, anti-inflammatory medications (NSAIDs, corticosteroids, etc.) or immunosuppressive therapies within the 4 weeks prior (for DG patients only)
- 3) Opioid use within the last 4 weeks of gastric emptying scintigraphy
- 4) 4. Prior gastric surgery
- 5) 5. History of IBD, celiac disease, eosinophilic gastroenteritis, microscopic colitis

Dietary, fluid and other restrictions:

During recruitment, informed consent review, and visits, the subjects were informed and reminded of the following restrictions:

1. No alcohol for 72 hours before 1st visit and until after end of study period
2. Use of tobacco products (last 3 months)

Sites where research will be performed

Mayo Clinic in Rochester, Minnesota

b. Sources of research materials

Research material will be the ¹¹C ER 176 PET/CT images, upper endoscopy with gastric muscle biopsies and cells derived from the biopsies. Additionally, questionnaire responses and medical records will be research materials. Results will be maintained in the research laboratories that are ultimately the sole responsibility of the PI, and will be accessed by a secure password available only to authorized study personnel. Data will be merged for studies of associations by the biostatistician. All of the information collected in this study will be for research purposes only.

c. Potential risks

The potential risks associated with the study are those associated with completing questionnaires, ¹¹C ER 176 PET/CT scan and EUS with biopsies. EUS-guided core biopsy is a safe procedure associated with a low risk of adverse events. Mild self-limiting serosal bruising and/or localized hematoma formation at the sites of EUS biopsies were reported in a small cohort of patients with gastroparesis who underwent EUS-guided FNA biopsy of the gastric muscle. Questionnaires come with a risk of privacy erosion and emotional distress. However, the

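### Diabetes without gastroparesis is the only arm that users of anti-inflammatory or immunosuppressive drugs may enter, so its uptake data are open to avoidable confounding

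*Combined protocol and SAP*

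**What the plan says.** The opening of Section D plans 4 patients with DG, "4 patients with diabetes without gastroparesis" and 4 healthy volunteers. DG and diabetic patients share the criteria in Table 1, where one exclusion reads "Using anti-coagulants, anti-inflammatory medications (NSAIDs, corticosteroids, etc.) or immunosuppressive therapies within 4 weeks prior (for DG patients only"). Section F.1.a repeats it with the same restriction: "immunosuppressive therapies within the 4 weeks prior (for DG patients only"). Healthy volunteers have their own rule in Section D: they will "be screened to have no inflammatory disorders of the GI tract or use of anti-inflammatory or immunosuppressive therapies". That rule has no look-back window, and Section F.1.a does not repeat it.

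The exclusions for inflammatory bowel disease, celiac disease, eosinophilic gastroenteritis, microscopic colitis and prior gastric surgery carry no DG-only tag in either list, so they do cover the diabetic arm.

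On the comparison, Hypothesis 1 in Section A predicts higher uptake "in gastric body and antrum compared to matched controls", and the image analyses paragraph of Section D compares DG patients with controls. Neither says which control arm is meant. The endpoints paragraph makes stomach biodistribution of the tracer the primary endpoint and says that the study will supply means and SDs for a larger one.

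**The concern.** The protocol's preliminary studies tie the tracer's target to activated, pro-inflammatory macrophages. Drugs that act on inflammation could plausibly change what the scan measures. If such drugs are kept out of two arms and allowed in the third, a difference in uptake between DG and diabetes alone could partly reflect medication.

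The diabetic arm is the one included to help separate gastroparesis from diabetes, which DG versus healthy volunteers cannot do. Its mean and SD are also among the figures that a larger study would draw on. With 4 people per arm, a single user is a quarter of the group.

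The direction is open. If the drugs suppress the signal, users in the diabetic arm would widen the gap from DG. If users have higher uptake because of the condition being treated, they would narrow it.

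**Working it through.** **Step 1: medication rule by arm**

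| Arm | n | Rule on anti-inflammatory or immunosuppressive drugs | Source |
|---|---|---|---|
| DG | 4 | Excluded, 4-week window | Table 1; F.1.a |
| Diabetes without gastroparesis | 4 | None | Table 1 and F.1.a, by the DG-only tag |
| Healthy volunteers | 4 | Screened for no use, no window | Section D, opening |

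The two lists agree, so this is a stated rule and not a slip in one table. The 4-week window names no reference event, whereas the opioid item is tied to scintigraphy. Endoscopy may fall well away from imaging ("The endoscopy will be performed within 12 weeks of the" scan), so even for DG it is unclear whether the window covers the scan.

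**Step 2: outputs exposed.** DG versus diabetes alone, and the diabetic-arm mean and SD, are exposed. DG versus healthy volunteers is not, because both of those arms restrict use.

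**Step 3: chance of at least one user.** The documents give no prevalence, so p is assumed. The chance is 1 − (1 − p)^4: 34% at p = 0.1, 59% at 0.2, 76% at 0.3 and 94% at 0.5.

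**Step 4: size of the shift.** The plan states no effect size, SD, alpha or power, so there is no figure of its own to reproduce. All inputs here are assumed: no true difference, one user among the 4 diabetic participants, a user's uptake differing by r = 0.2 or 0.5 as a fraction, and a between-subject CV of 0.2 or 0.4.

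- DG/diabetic ratio = 4/(4 − r) if the drug lowers uptake, or 4/(4 + r) if it raises it.
- SE of the ratio near 1 = CV × √(1/4 + 1/4) = 0.141 at CV 0.2 and 0.283 at CV 0.4.

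| Assumed effect | Ratio | Shift in SEs, CV 0.2 | Shift in SEs, CV 0.4 |
|---|---|---|---|
| Lowers by 20% | 1.053 | 0.37 | 0.19 |
| Lowers by 50% | 1.143 | 1.01 | 0.51 |
| Raises by 20% | 0.952 | 0.34 | 0.17 |
| Raises by 50% | 0.889 | 0.79 | 0.39 |

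One of the eight combinations reaches one SE and the others are below 0.8. On the log scale the largest is ln(4/3.5)/0.141 = 0.94.

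**Step 5: the diabetic-arm SD.** With one user, the expected sample variance relative to no user is 1 + r²/(4CV²) under additive noise, which gives 1.06 to 2.56. Under constant CV it is [3 + (1 ± r)²]/4 + r²/(4CV²), which gives 0.97 to 2.88. The answer depends on the noise model, so no particular effect on a later sample size follows.

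**The case against.** **The tag may be there for biopsy safety.** "Upper endoscopy will be performed only on DG patients only", and the item also lists anti-coagulants. This may explain part of the tag, but the documents do not say so. It would not explain the screen in healthy volunteers, who have no biopsy. Whatever the reason, the imaging comparison is left with unequal rules.

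**The comparator is most naturally the healthy volunteers.** They are the only group called matched (Section D, opening; F.1.a). The anticipated-results paragraph names only them, and the timeline counts only DG patients and healthy volunteers. This stands. A reader might infer that the test of Hypothesis 1 is itself biased, or that a contrast against pooled controls is. The text does not support either: the contrast it most naturally names is untouched, and nothing in the protocol proposes pooling.

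**Part of the gap is already closed.** The gut-inflammatory-disease exclusions apply to diabetic patients, so what remains concerns medication only. This also stands.

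**The DG-versus-diabetic contrast is not clean in any case.** No matching is stated for the diabetic arm, and the gastric emptying test is required of DG patients only. That is correct, and medication is one weakness among several. It is, however, one that can be removed cheaply.

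**The harm is conditional and small.** The drug effect is assumed, the study is about feasibility and no test is planned. This limits the severity. It does not remove the point, because a shift of this size could not be recognised from the uptake values; it can be seen only if use is recorded. Use is probably retrievable from the screening history and from records ("questionnaire responses and medical records will be research materials"), but nothing commits the study to capturing it over a common window or reporting it.

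**Conclusion.** The point holds as a modest one. Followed exactly, the plan can admit users of these drugs to the diabetic arm alone, which leaves DG versus diabetes without gastroparesis, and the diabetic-arm mean and SD, open to avoidable confounding.

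That the rule is unequal is certain from the text. That it would bias uptake rests on an assumed drug effect whose direction and size the documents do not give. Under the assumptions tried, the shift is mostly well below one standard error at 4 per arm.

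A reader might go further and infer inflated error rates or a predictable error in a later sample size. Neither is supported: the plan states no test, and the effect on the variance can go either way. What is at stake is whether the description of the diabetic arm can be read without medication as a rival explanation. Minor to moderate.

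**What to change.** Either of two changes would do.

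1. Reconcile the opening of Section D, Table 1 and Section F.1.a so that medication eligibility for the imaging comparison is the same in all three arms. This is done by selection of participants, with no drug stopped for it. If the DG-only tag is there for biopsy safety, say so. The cost is a slightly smaller pool from which to find 4 diabetic participants.
2. At minimum, record anti-inflammatory and immunosuppressive use for all 12 participants over one look-back window counted back from the PET scan. Report individual uptake values flagged by use in every arm, with a supplementary summary without users where numbers allow. The cost is one medication entry per participant, from sources already planned.

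The supplementary summary loses precision. Relative to 4 versus 4, the SE grows by √(1/4 + 1/3)/√(1/4 + 1/4) = 1.08 with one of the 4 diabetic participants set aside, and by √(1/4 + 1/2)/√(1/4 + 1/4) = 1.22 with two. With three set aside, one value is left and no SD can be estimated. Individual flagged values should therefore be the main report.

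With either option, state in the image analyses and endpoints paragraphs that DG versus diabetes without gastroparesis and DG versus healthy volunteers are reported as separate, unpooled contrasts. That costs only wording.

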Innovation: This proposal is innovative from both biological and technical standpoints. Strong animal and human data generated by our group and others demonstrate macrophage activation in gastroparesis. This has been mechanistically shown to play a role in gastric motor dysfunction via injury to ICC. There is currently no noninvasive way to determine immune dysregulation in the gastric muscle. More broadly, macrophage dysfunction also plays a role in other inflammatory disorders of the gut such as inflammatory bowel disease. Technological advancements in ligands for PET imaging have already led to emergence of its role in studying neuroinflammation as well as joint inflammation. We plan to use the latest generation TSPO radioligand, ¹¹C-ER176, for delineating macrophage activation in DG. We will validate imaging findings with state-of-art sampling of gastric muscle followed by isolation of immune cells and using single cell-based techniques to determine transcriptional changes in immune cells. If successful, these studies will provide pilot data for larger studies aimed at determining immune dysregulation in diabetic gastroenteropathy as well as other inflammatory GI disorders.

C. Preliminary Studies

Macrophage cell population in gastric muscle expresses TSPO: In preliminary studies, human gastric muscle tissues (idiopathic gastroparesis) were dissociated followed by magnetic separation and isolation of CD45⁺ immune cells. Libraries were prepared using 10x Genomics Library Kits and sequenced on HiSeq4000. The t-distributed stochastic neighbor embedding (t-SNE) plot revealed 12 clusters of CD45⁺ cells (**Figure 3a**). CD68, a type I transmembrane glycoprotein, heavily expressed in cells of monocyte/macrophage lineage forming a discrete cluster (**Figure 3b**). TSPO showed predominant expression in the CD68⁺ subset of cells (**Figure 3c**). This suggests that gastric muscle contains immune cells that are TSPO⁺, hence, providing proof-of-concept data that ¹¹C-ER176 PET imaging targeting TSPO should demonstrate uptake *in vivo* in humans. TSPO has been strongly associated with an activated or pro-inflammatory macrophage subtype. In a recent study, during M2 (anti-inflammatory) polarization, TSPO expression was decreased¹⁴. A TSPO antagonist enhanced anti-inflammatory polarization. Additional studies have also demonstrated TSPO being an imaging target for identifying pro-inflammatory macrophage milieu^{12, 19}.

[figure not shown]

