Endpoints and statistical analysis: The biodistribution of ¹¹C-ER 176 in the stomach using time activity curves and other described imaging metrics will be the primary endpoint. Correlative analysis will be done between biodistribution on ¹¹C-ER176 and pro-inflammatory markers on cellular expression using CyTOF. The proposed study will provide means and standard deviations for larger investigation in this area. Considering the robust expression of TSPO in gastric macrophages in our preliminary data, we expect to see uptake of TSPO ligand ¹¹C-ER 176 in the gastric muscle.

Anticipated results, potential pitfalls and alternative strategies: We anticipate finding that patients with DG will have significantly higher PET uptake of ¹¹C-ER176 compared to healthy volunteers. Additionally, we anticipate that the uptake will strongly associate with upregulation of TSPO and other pro-inflammatory markers like Ly6C and downregulation of anti-inflammatory markers like CCR2, CX3CR1 and CD206. Most second-generation TSPO radioligands have varying degrees of sensitivity to the single nucleotide polymorphism rs6971 in the TSPO gene⁴⁰, and this genotype sensitivity may vary depending upon the organ where it is expressed²². Therefore, some subjects who are low-affinity binders are excluded from analyses and the remaining subjects are corrected for being either high- or mixed-affinity binders. On the other hand, ¹¹C-ER176, a third-generation ligand, has shown little *in vitro* sensitivity to rs6971. However, *in vivo*, ¹¹C-ER176 was found to be sensitive to rs6971. Nevertheless, it allowed quantitation even in low affinity binders and had high non-displaceable binding potential, which suggests that its relative *in vivo* sensitivity to rs6971 may not impact clinical imaging²². Due to the small sample size of this feasibility study, we will be unable to select subjects with varying TSPO affinity genotype. However, if we see insufficient binding, we will determine the genotype.

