Timeline: We plan to finish recruitment of 4 DG patients and 4 healthy volunteers including ¹¹C-ER176 PET/CT as well as endoscopic ultrasound with core biopsies within 7 months. Images will be processed in parallel. The next 3 months will be used for finalizing image analysis as well as CyTOF for the immune markers followed by manuscript submission in the last 2 months. Considering the large volume of DG patients seen at Mayo Clinic and strengths of the PI's team in recruitment, we are confident we will be able to recruit. The PI's laboratory is housed within the Enteric Neuroscience Program (Director, ██████████) and the group has considerable experience in cellular and molecular assessment of human gastric tissue^{1, 5, 6, 10, 41-43}. The nuclear medicine group at Mayo Clinic has a long-standing track record and expertise in studies of this nature as well as an established infrastructure to perform the dynamic PET scanning. The preliminary data, availability of participants, and the expertise of the investigating groups (GI, radiology) will ensure that the proposed studies are completed within the 1-year time frame allowing time for dissemination of results and generating data for a larger grant proposal.

E. Literature Cited

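### Uptake is predicted to track tissue TSPO, but the listed CyTOF panel omits TSPO and the biopsy methods give no other TSPO readout

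*Combined protocol and SAP*

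**What the plan says.** The prediction is in Section D, under anticipated results: "the uptake will strongly associate with upregulation of TSPO and other pro-inflammatory markers like Ly6C". The same sentence expects CCR2, CX3CR1 and CD206 to go down. The paragraph on endpoints and statistical analysis, just before it, plans to correlate tracer biodistribution with "pro-inflammatory markers on cellular expression using CyTOF".

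The tissue assay is set out in Section D, in the paragraph on how macrophages in the stomach are assessed. It begins: "After tissue dissociation, using technique similar to that shown in the preliminary data, cells will be sorted and profiled using the Fluidigm". The instrument is a CyTOF system. On the labelling, the plan states: "cellular subtypes will be identified and counted after labeling with a panel of 32 antibodies to distinguish monocytes and tissue myeloid cells". Every antibody is then named, and TSPO is not among them.

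Two other places bear on how TSPO might be read in tissue. The Innovation paragraph of Section B says that imaging will be validated by sampling gastric muscle, followed by "isolation of immune cells and using single cell-based techniques to determine transcriptional changes in immune cells". In Section C, the preliminary TSPO finding in gastric CD45+ cells came from sequencing: "Libraries were prepared using 10x Genomics Library Kits and sequenced on HiSeq4000". That tissue was from idiopathic, not diabetic, gastroparesis.

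**The concern.** TSPO is what the tracer binds, and imaging the stomach in diabetic gastroparesis is described as a new use of it. The one gastric TSPO reading that the documents report is from idiopathic gastroparesis. The biopsies in this study are therefore the plan's opportunity to see whether the target is raised in the diabetic stomach, and raised where the scan shows signal.

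The sampling scheme suits that question. Cores come from a PET-targeted site and an uninvolved site or, where there is no clear signal, from antrum and body. Without a TSPO reading, this contrast describes which immune cells are present but not whether the tracer's target differs between sites.

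The gap also limits what can be learned from a weak scan. If binding is insufficient, the stated step is to determine the TSPO genotype. Genotype bears on binding affinity. It does not show whether the target was scarce in that tissue.

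**Working it through.** This is a comparison of texts. The plan states no power or alpha for the correlative analysis, and none is needed here.

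**1. The plan's own figure.** The panel is stated as 32 antibodies. Splitting the printed list at its commas gives 33 entries, one more than stated. Counting IL2RA and CD25 as a single target would give 33 − 1 = 32, although the documents do not say that this is the reason. TSPO is absent on either count, so nothing below depends on the difference.

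**2. The predicted markers against the list.**

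| Marker in the prediction | Predicted direction with uptake | On the listed panel |
|---|---|---|
| TSPO | up | no |
| Ly6C | up | yes |
| CCR2 | down | yes |
| CX3CR1 | down | yes |
| CD206 | down | yes |

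Four of five are present. The missing one is the tracer's target. CD68, the macrophage marker that overlapped with TSPO in the preliminary data, is not listed either.

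**3. Does the correlative analysis cover TSPO?** The prediction classes TSPO with the pro-inflammatory markers, and the analysis paragraph says that this class will be related to uptake by CyTOF. On the plan's own classification, TSPO falls within an analysis whose named platform, as listed, cannot read it.

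**4. Does the biopsy method bring in sequencing by reference?** The paragraph on gastric macrophages does point back to the preliminary data, where sequencing was used. But the reference is attached to tissue dissociation, and the sentence then names CyTOF for profiling. It carries over how cells are freed from tissue, not how they are read.

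**5. Could TSPO come from elsewhere in the plan?**
- The blood work in Section D could: "PBMCs will be isolated and their transcriptional and epigenomic profile will be studied". But these are circulating cells and give no gastric value.
- The consent text in Section F mentions sharing sequencing data without saying whether they come from biopsies or blood.
- The Innovation commitment does concern gastric-muscle immune cells and could supply TSPO. It names no TSPO readout, and the biopsy methods contain no matching step.

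**6. Size of the gap.** Endoscopy is for the diabetic gastroparesis group only, which is 4 patients. Assuming two sampled sites per patient and one value per site, 4 × 2 = 8 site-level TSPO values would be missing, in matched pairs within patients. The documents do not give the number of passes per site.

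**The case against.** The strongest reply is that the plan already commits to an assay that can read TSPO. The Innovation paragraph is written in the future tense, concerns gastric muscle, and is followed directly by preliminary data in which sequencing of gastric immune cells located TSPO. The biopsy methods specify CyTOF but do not rule out sequencing. This stands in part. A reader might infer that the study has no means of measuring tissue TSPO, or that the transcriptional work was dropped. The documents do not support either inference.

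Nor does silence elsewhere in Section D show that it was dropped. The timeline mentions "CyTOF for the immune markers followed by manuscript submission in the last 2 months" and no sequencing, and the endpoint paragraph is equally brief. But neither mentions the blood-cell profiling to which the plan plainly commits. These are abbreviated summaries. The omission that carries weight is the one in the paragraph that specifies the tissue assay.

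A second reply is that the panel exists to tell myeloid cells from other immune cells, so leaving out the tracer's target is no fault in itself. That is fair for a cell-typing panel. It answers less well once the same platform is named for correlating uptake with pro-inflammatory markers, and TSPO is the first of those named.

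A third is that no hypothesis or endpoint rests on TSPO. This is correct and limits the weight of the point. Hypothesis 2 concerns a shift in macrophage milieu, and Section F.4 describes the tissue validation in terms of cellular markers of pro- or anti-inflammatory macrophages.

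**Conclusion.** The point holds as a mismatch between a stated prediction and the assay specified to examine it. One of five predicted markers, the tracer's own target, is not on the listed panel, and the biopsy methods contain no other step that would measure it. If those methods are followed as written, the uptake–TSPO prediction will be neither supported nor contradicted.

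The consequence is confined to an exploratory reading in a pilot. The primary endpoint, tracer biodistribution in the stomach, is untouched. A reader might go further and infer that Hypothesis 2 or the tissue validation fails without TSPO. The documents do not support that: neither is worded to require TSPO, and the other four predicted markers are on the panel. Nor does the plan claim that the biopsies will prove the PET signal to be TSPO, so no such claim needs correcting.

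The conclusion assumes that the printed list is the whole panel and that the biopsy paragraph governs how tissue is processed. If the transcriptional assay is in fact to be run on the biopsies with TSPO as a readout, what remains is to write it into that paragraph.

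**What to change.** Before the first biopsy is processed, add TSPO to the CyTOF panel and name macrophage TSPO as a tissue variable in the correlative analysis. Report it descriptively: each patient's value at each biopsy site, beside the PET metric for the same site.

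This uses tissue already being collected and needs no further participant or procedure. The cost is reagent and titration work and possibly a panel channel. The documents do not state spare panel capacity or prices, so the size of that cost is unknown.

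If TSPO is to come from the single-cell transcriptional assay instead, state that assay and its TSPO readout in the paragraph on gastric macrophages. That paragraph should also say how cells are shared between the two assays. Sharing would leave fewer cells for each if yield is limited, and the documents give no yields.

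If neither is feasible, take TSPO out of the anticipated tissue associations. That is only a text change. It makes the plan consistent but adds no information about the target.

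While editing, reconcile the stated 32 antibodies with the 33 entries printed.
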